1.0 PROTOCOL SUMMARY

1.1 Synopsis

Protocol Synopsis	
Protocol Title	A Randomized, Open-label, Active-controlled Study Evaluating the Efficacy and Safety of Dose Conversion from a Long-acting Erythropoiesis-stimulating Agent (Mircera [®]) to Three Times Weekly Oral Vadadustat for the Maintenance Treatment of Anemia in Hemodialysis Subjects
Protocol Number	AKB-6548-CI-0039
Phase of Development	3b
Indication	Anemia associated with chronic kidney disease (CKD)
Investigational Product	Vadadustat; 300 mg tablets
Reference Therapy, as applicable	Methoxy polyethylene glycol-epoetin beta (Mircera), F. Hoffman-La Roche Ltd.
Study Population	The study population will consist of subjects \geq 18 years of age and receiving chronic, outpatient in-center hemodialysis three times weekly (TIW), requiring erythropoiesis-stimulating agent (ESA) treatment and are on maintenance treatment currently receiving Mircera and with mean of 2 Screening hemoglobin (Hb) values between 8.5 and 11.0 g/dL (inclusive).
Number of Study Sites	Approximately 50 investigative sites in the United States (US) at outpatient hemodialysis center.
Planned Number of Subjects	Approximately 450 subjects.
Rationale	During prior clinical trials, vadadustat has demonstrated dose proportional pharmacokinetic (PK) and dose dependent pharmacodynamics (PD). Vadadustat showed dose-dependent increases in erythropoietin (EPO) concentrations in Phase 1 and Phase 2 studies. The changes in EPO have been accompanied by an increase in reticulocytes and Hb as well as increases in total iron binding capacity (TIBC) and decreases in hepcidin and ferritin. Overall, the safety profile for vadadustat has been acceptable and has supported further development. Akebia is developing vadadustat as a treatment for anemia associated with CKD in adult patients. The development program to date included a number of phase 1, 2, and 3 clinical trials in both populations. A majority of trials studied once daily (QD) dosing. TIW dosing is supported by an earlier completed clinical trial involving TIW dosing and PK-PD modelling data. The rationale for this trial is to obtain safety and efficacy data that supports DD-CKD patients switching from Mircera to vadadustat TIW.
Primary Objectives	The primary objective of the study is to demonstrate the efficacy and safety of vadadustat administered TIW compared to long acting ESA (Mircera) for the maintenance treatment of anemia in hemodialysis subjects.
Efficacy Endpoints	
Primary:
 
Primary efficacy endpoint is mean change in Hb between Baseline (average pretreatment Hb) and the primary evaluation period (average Hb from Weeks 20 to 26, inclusive). 
Secondary:
 
Secondary efficacy endpoint is mean change in Hb between Baseline (average pretreatment Hb) and the secondary evaluation period (average Hb from Weeks 46 to 52, inclusive).

Other Endpoints	
 Proportion of subjects having a Hb value within the target range (10.0 to 11.0 g/dL) during the primary evaluation period (Weeks 20 to 26). Proportion of subjects having a Hb value within the target range (10.0 to 11.0 g/dL) during the secondary evaluation period (Weeks 46 to 52).
Safety Endpoints	
 Treatment-emergent adverse events (AEs) and Serious Adverse Events (SAEs). Proportion of subjects receiving red blood cell (RBC) transfusions from Baseline to Week 26 Proportion of subjects receiving RBC transfusions from after Week 26 to Week 52. Proportion of subjects with Hb >11.0, Hb >12.0, >13.0, or >14.0 g/dL. Proportion of subjects with Hb <7.0, <8.0, <9.0, or <10.0 g/dL. Proportion of subjects with Hb increase >1.0 g/dL within any 2-week interval or >2.0 g/dL within any 4-week interval.
PK/PD Endpoints	
The PK endpoints include the following:
 
 Maximum observed concentration (C_{\max}) Pre-dose trough concentration (C_{tau}) 
The PD endpoints include the following:
 
 EPO Reticulocyte count Markers of iron metabolism (including iron, ferritin, total iron binding capacity [TIBC]).
Methodology (study design)	
A multi-center, randomized, open-label, active-controlled study of the efficacy and safety of conversion from long-acting ESA (Mircera) to vadadustat TIW for the maintenance treatment of anemia in hemodialysis patients. Following a Screening period of up to 8 weeks (56 days), subjects who meet all inclusion and none of the exclusion criteria, Mircera will be discontinued and subjects will be randomized 1:1:1 to vadadustat 600 mg TIW, vadadustat 900 mg TIW, or to remain on Mircera according to the dialysis center's protocol.
 
Randomization will be stratified by dialysis organization:
 
Following randomization, there will be 2 periods during the study:
 
 Conversion and Maintenance Period (Weeks 0 to 52): conversion to vadadustat TIW or to remain on Mircera (Weeks 0 to 20). There will be a primary efficacy evaluation period (Weeks 20 to 26) and a secondary efficacy evaluation period (Weeks 46 to 52). Safety Follow-up Period (Early Termination [ET] and Follow-Up): post-treatment safety follow up visit (ET/End of Treatment [EOT] +4 weeks) either in person or via telephone.
Study Duration	Individual subjects will participate in the study for up to 64 weeks, including a Screening Period of up to 8 weeks, a 52-week Treatment Period and a 4-week Safety Follow-Up Period.
Key Inclusion and Exclusion Criteria	Subjects must meet the following inclusion criteria: 
 ≥18 years of age. Receiving chronic, outpatient in-center hemodialysis TIW for end-stage kidney disease for at least 12 weeks prior to Screening Visit (SV)1. Currently maintained on Mircera (≤250 µg/month) with at least 2 doses

[figure not shown]
	
received within 8 weeks prior to SV2.
 
4. Mean screening Hb between 8.5 and 11.0 g/dL (inclusive), as determined by the average of 2 Hb values measured by the central laboratory at least 4 days apart between SV1 and SV2.
 
5. Serum ferritin \geq100 ng/mL and transferrin saturation (TSAT) \geq20% during Screening.
 
6. Folate and vitamin B₁₂ measurements \geq lower limit of normal during Screening.
 
Subjects must not meet any of the following exclusion criteria:
 
1. Anemia due to a cause other than CKD (e.g., sickle cell disease, myelodysplastic syndromes, bone marrow fibrosis, hematologic malignancy, myeloma, hemolytic anemia, thalassemia, or pure red cell aplasia).2. Clinically meaningful bleeding event in opinion of investigator within 8 weeks prior to Baseline.3. RBC transfusion within 8 weeks prior to Baseline.4. Having received any doses of darbepoetin alfa (Aranesp[®]) within the past 4 weeks prior to Baseline.5. Having any epoetin alfa (Epogen[®]) within the past 1 week prior to Baseline.6. Anticipated to discontinue hemodialysis during the study.7. Judged by the Investigator that the subject is likely to need rescue therapy (ESA administration or RBC transfusion) immediately after enrollment in the study.8. History of chronic liver disease (e.g., chronic infectious hepatitis, chronic autoimmune liver disease, cirrhosis or fibrosis of the liver).9. Aspartate aminotransferase (AST)/serum glutamic oxaloacetic transaminase (SGOT), alanine aminotransferase (ALT)/serum glutamic pyruvic transaminase (SGPT), or total bilirubin >2 x upper limit of normal (ULN) during Screening. Subjects with a history of Gilbert's syndrome are not excluded.10. Current uncontrolled hypertension as determined by the Investigator that would contraindicate the use of an ESA.11. Acute coronary syndrome (hospitalization for unstable angina or myocardial infarction), surgical or percutaneous intervention for coronary, cerebrovascular or peripheral artery disease (aortic or lower extremity), surgical or percutaneous valvular replacement or repair, sustained ventricular tachycardia, hospitalization for heart failure (HF) or New York Heart Association Class IV HF, or stroke within 12 weeks prior to or during Screening.12. History of new, active or recurrent malignancy within 2 years prior to and during Screening or currently receiving treatment or suppressive therapy for cancer. Subjects with treated basal cell carcinoma of skin, curatively resected squamous cell carcinoma of skin, or treated cervical carcinoma in situ are not excluded.13. History of deep vein thrombosis or pulmonary embolism within 12 weeks prior to or during Screening14. History of hemosiderosis or hemochromatosis.15. History of prior organ transplantation (subjects with a history of failed
--	---

	
kidney transplant or corneal transplants are not excluded).
 
16. Scheduled organ transplant from a living donor and subjects on the kidney transplant wait-list who are expected to receive a transplant within 6 months.
 
17. History of a prior hematopoietic stem cell or bone marrow transplant (stem cell therapy for knee arthritis is not excluded).
 
18. Known hypersensitivity to vadadustat, Mircera, or any of their excipients.
 
19. Use of an investigational medication or participation in an investigational study within 30 days or 5 half-lives of the investigational medication (whichever is longer), prior to Screening (subjects may participate in another concurrent study only if that study is a non-interventional, observational investigation).
 
20. Current exposure to any hypoxia-inducible factor prolyl-hydroxylase (HIF-PH) inhibitor or prior exposure to vadadustat.
 
21. Subjects with bilateral native nephrectomy.
 
22. Noncompliance with dialysis session attendance defined as missing more than 1 dialysis session within 8 weeks prior to Baseline.
 
23. Active Severe Acute Respiratory Syndrome-Related Coronavirus (SARS-CoV-2) during Screening.
 
24. Females who are pregnant or breastfeeding during Screening or are planning to become pregnant and breastfeeding during the study period, and for 30 days after the final study drug administration.
 
25. Women of childbearing potential who are unable or unwilling to use 2 acceptable methods of contraception* starting at Screening, throughout the study period and for 45 days after the final study drug administration.
 
26. Female subjects of childbearing potential who plan to donate ova during the study, and for 30 days after the last dose of study drug.
 
27. Non-vasectomized male subjects who are unable or unwilling to use an acceptable method of contraception* from time of first dose of study drug until 30 days after the last dose of the study drug.
 
28. Male subjects who plan to donate sperm during the study and for at least 30 days after the last dose of study drug.
 
29. Any other reason, which in the opinion of the Investigator, would make the subject not suitable for participation in the study.
 
*Acceptable forms of contraception include:
 
• Established use of oral, injected or implanted hormonal methods of contraception• Placement of an intrauterine device or intrauterine system• Barrier methods of contraception: condom or occlusive cap (diaphragm or cervical/vault caps) with spermicidal foam/gel/film/cream/suppository.
Safety Oversight	An Independent Data Monitoring Committee (IDMC) will be established to review and discuss the available study data as subjects are enrolled and followed. The IDMC will meet approximately twice per year throughout the course of the study. The IDMC will be unblinded and will include, at a minimum 2 physicians and a biostatistician. The discussions of the IDMC will include a review of key safety data (i.e., AEs, vital sign measurements, and laboratory assessments). Hepatic cases will be adjudicated by a hepatic panel of experts.
Statistical considerations	The primary efficacy endpoint is defined as the mean change in Hb between Baseline (average pretreatment Hb) and the primary evaluation period (average Hb from Weeks 20 to 26, inclusive).


a. General analysis plan
 
b. Rationale for number of subjects
	
The primary analysis of the primary endpoint will use the randomized population. Analysis of covariance (ANCOVA) with multiple imputation for missing data will be used to calculate the 95% confidence interval (CI) of the difference in mean change in Hb from baseline to the primary evaluation period between the vadadustat group and Mircera® control group, with a randomization stratification factor and Baseline Hb as covariates.
 
Noninferiority of vadadustat will be established if the lower limit of this CI is ≥ -0.75 g/dL.
 
A hierarchical testing scheme will be used to correct for the multiplicity of the 2 comparisons of the primary efficacy endpoint: comparison between vadadustat TIW 600 mg versus Mircera and comparison between vadadustat TIW 900 mg versus Mircera .
 
• Step 1: comparison between vadadustat TIW 900 mg versus Mircera If the noninferiority of vadadustat is established in step 1, then move to the step 2;• Step 2: comparison between vadadustat TIW 600 mg versus Mircera 
For the primary efficacy analysis, it will be assumed that the difference in mean change from Baseline in Hb for vadadustat will be the same as the active control, Mircera, and the common standard deviation for the mean change from Baseline will be assumed to be 1.2 g/dL. The noninferiority margin of -0.75 g/dL will be used (for vadadustat minus Mircera). With the 1:1:1 randomization ratio of vadadustat 600 mg TIW, vadadustat 900 mg TIW, and Mircera, approximately 150 subjects in each arm, the noninferiority test will have >90% power with consideration of a 30% drop out rate.
 
In addition to the final analysis which will take place when all subjects have completed study and will include all data collected, the 26-week efficacy and safety data may be summarized after the last patient completes the primary efficacy period (Week 26). As the study conduct and final analyses of primary efficacy endpoint will not be modified by this analysis, no alpha adjustment is proposed. The decision about whether this 26-week analysis would be conducted and details about the analysis will be described in the statistical analysis plan (SAP).

--	---

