- If a dose increase or decrease is required to achieve and maintain Hb levels within the target range of 10.0 to 11.0 g/dL inclusive, dose is adjusted by 1 dose level (vadadustat 300 mg).
- A one-time dose increase after the first 2 weeks of dosing after randomization is allowed. Thereafter, in general, do not increase the dose more frequently than once every 4 weeks.
 - A subject's dose may be increased by 1 dose level (300 mg TIW) if the subject has a decline in Hb ≥ 0.5 g/dL from Baseline in the first 2-week period (the initial period from Baseline to Week 2 following conversion from Mircera) and if Hb is < 10.0 g/dL.
- Reduce the dose in the setting of a rapid rise in Hb (defined as > 1.0 g/dL in any 2-week period or > 2.0 g/dL in any 4-week period).
- Reduce the dose in the setting of Hb > 11.0 g/dL.
- Interrupt the dose in the setting of a Hb > 12.0 g/dL until Hb value falls below 11.0 g/dL. After Hb falls below 11.0 g/dL, restart study drug at a lower dose.

The minimum dose of vadadustat will be 300 mg TIW (1 tablet TIW) and the maximum dose will be 1200 mg TIW. Subjects whose dose of vadadustat is interrupted due to elevated Hb will continue in the study. Unless contraindicated, treatment will be resumed whenever possible and assessed at every visit following study drug interruption.

Mircera will be administered as standard of care. Dose adjustments will be made according to the dialysis center's protocol.

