3.3 SAMPLE SIZE DETERMINATION

For the primary efficacy analysis, it is assumed that the difference in mean change from Baseline in Hb for vadadustat will be the same as the active control, Mircera, and the common standard deviation for the mean change from Baseline will be assumed to be 1.2 g/dL. The noninferiority margin of -0.75 g/dL will be used (for vadadustat minus Mircera). With the 1:1:1 randomization ratio of vadadustat 600 mg TIW, vadadustat 900 mg TIW, and Mircera, and approximately 150 subjects in each arm, the noninferiority test will have >90% power with consideration of a 30% drop out rate.

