6.11.2 Primary Efficacy Analyses

The primary efficacy endpoint is defined as the mean change in Hb between Baseline (average pretreatment Hb) and the primary evaluation period (average Hb from Weeks 20 to 26, inclusive).

The primary analysis of the primary endpoint will use the randomized population with imputation of data. All intercurrent events will be handled by treatment policy strategy ([Section 6.11.1](#)). Unobserved data after intercurrent events, including Hb outcomes and any covariates to be used in the models, will be imputed with the randomized treatment group to which the subject was randomized using multiple imputation under fully conditional specification (FSC) method as described in [Appendix B](#). Data up to

scheduled visit of week 26 will be included in the primary efficacy analyses. Analysis of covariance (ANCOVA) as described in [Appendix A](#) will be used to calculate the LS mean (SE) by treatment group and LS mean difference (SE), 95% confidence intervals (CI) of the difference in mean change in Hb from baseline to the primary evaluation period between the vadadustat groups and Mircera control group, with the randomization stratification factor (Dialysis organization) and Baseline Hb as covariates.

Treatment comparisons will be performed between the vadadustat and Mircera groups. Subjects in the vadadustat starting dose groups of 600 mg or 900 mg TIW will have their doses adjusted to maintain Hb levels of 10.0 to 11.0 g/dL following the protocol's dosing algorithm.

- Noninferiority of vadadustat will be established if the lower limit of 2-sided CI is greater or equal to -0.75 g/dL for combined vadadustat dosing groups minus Mircera.

If the lower limit of the 2-sided 95% confidence interval for the difference between the mean Hb change from baseline to Weeks 20 to 26 in the vadadustat group and the mean Hb change from baseline in the Mircera group is above zero, superiority will have been established and the finding will be interpreted as providing evidence of a greater change from baseline in Hb for vadadustat relative to the control arm. Because the same 95% confidence interval is used to the superiority test, no adjust of multiplicity is needed.

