7. CHANGES TO PROTOCOL-PLANNED ANALYSES

Removed the hierarchical testing scheme for both primary and secondary efficacy endpoints. Treatment comparisons will be performed between vadadustat (combining the 2 randomized groups with starting dose of 600mg and 900mg) and Mircera groups. Subjects in the vadadustat starting dose groups of 600 mg or 900 mg TIW will have their doses adjusted to maintain Hb levels of 10.0 to 11.0 g/dL following the protocol's dosing algorithm. The subgroup analysis with different starting dose with vadadustat vs. Mircera will be considered as exploratory analyses.

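### The SAP's pooled 2:1 primary comparison should use a variance estimate that stays valid if Hb variability differs between vadadustat and Mircera

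*Protocol*

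**What the plan says.** The protocol (synopsis and section 10.5.2) plans an ANCOVA after multiple imputation, with baseline Hb and the stratification factor as covariates. It compares 900 mg and then 600 mg with Mircera in a fixed order: "Analysis of covariance (ANCOVA) with multiple imputation for missing data will be used to calculate the 95% confidence interval (CI". Each comparison is 1:1, about 150 against 150.

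SAP section 7 drops the hierarchy and makes the comparison one of vadadustat, "combining the 2 randomized groups with starting dose of 600mg and 900mg", against Mircera. SAP 6.11.2 sets the criterion: "lower limit of 2-sided CI is greater or equal to -0.75 g/dL for combined vadadustat dosing groups minus Mircera". With 1:1:1 randomization this is about 300 against 150. SAP section 1 says that the SAP prevails over the protocol.

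SAP 6.11.2 refers to Appendix A for the ANCOVA and names dialysis organization and baseline Hb as covariates. It reuses the same interval for superiority at zero, and 6.11.3 carries the method to Weeks 46 to 52. The visible text mentions no robust or arm-specific variance, and no sensitivity analysis in 6.11.2.1 is described as relaxing equal variance between arms. The Appendix A model code cannot be read in the public copy.

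The only statement of a shared SD is in the sample-size text: "the common standard deviation for the mean change from Baseline will be assumed to be 1.2 g/dL".

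The arms are titrated differently (protocol 7.1.2). Vadadustat follows protocol guidelines in 300 mg steps. For the control arm, "Mircera will be administered as standard of care", with adjustments under each dialysis center's protocol.

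**The concern.** With two equal groups, a common-variance standard error is right even if the SDs differ, because the pooled variance weights both arms equally. At 2:1 it is not. The larger arm dominates the pooled variance, while the smaller arm contributes most of the sampling variance of the difference. The interval is then too narrow if the smaller arm (Mircera) is the more variable one, and too wide if the larger arm is.

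The SAP's move to a pooled comparison therefore introduced a sensitivity that the protocol's per-dose tests, fitted as two-group models, would not have had. The trial's one formal noninferiority decision, the superiority claim and the secondary analysis all rest on intervals of this kind. Too small a standard error raises the false-noninferiority rate above 2.5% one-sided; too large a one gives away precision.

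**Working it through.** **Inputs from the documents.** Margin -0.75 g/dL; two-sided 95% CI (one-sided 2.5%); planning SD 1.2 g/dL; true difference 0; about 150 per arm; 30% dropout; pooled comparison 300 against 150.

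**Assumed.** Arm-specific SDs, which the documents do not give. Ratios of 1.2 and 1.4 in either direction are the main cases, with 1.2 against 1.8 as a wider one.

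**Step 1: the plan's own figure.** At 150 × 0.7 = 105 per arm, SE = 1.2 × √(2/105) = 0.166. Then 0.75/0.166 − 1.96 = 2.57, a power of 99.5%. The stated power above 90% is correct. For the pooled test at 210 against 105, SE = 1.2 × √(1/210 + 1/105) = 0.143, and 0.75/0.143 − 1.96 = 3.27, a power of 99.9%. Power is not the issue.

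**Step 2: model SE against true SE at 300:150.**
- Pooled variance: s²p = (300·s²V + 150·s²M)/450
- Model SE = √[s²p(1/300 + 1/150)] = √(0.01·s²p)
- True SE = √(s²V/300 + s²M/150)
- One-sided error at the margin = Φ(−1.96 × model SE / true SE)

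Example, SDs 1.0 (vadadustat) and 1.2 (Mircera): s²p = (2 × 1.00 + 1.44)/3 = 1.147, so model variance is 0.01147. True variance is 1/300 + 1.44/150 = 0.01293. The ratio of SEs is 0.94, and Φ(−1.96 × 0.94) is about 3.3%.

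| SD vadadustat | SD Mircera | Model SE | True SE | Ratio | One-sided error | Half-width error, 1.96 × (model − true) |
|---|---|---|---|---|---|---|
| equal | equal | – | – | 1.00 | 2.5% | 0 |
| 1.0 | 1.2 | 0.107 | 0.114 | 0.94 | 3.3% | −0.013 |
| 1.0 | 1.4 | 0.115 | 0.128 | 0.90 | 3.9% | −0.026 |
| 1.2 | 1.8 | 0.143 | 0.162 | 0.88 | 4.2% | −0.039 |
| 1.2 | 1.0 | 0.114 | 0.107 | 1.06 | 1.9% | +0.013 |
| 1.4 | 1.0 | 0.128 | 0.115 | 1.11 | 1.4% | +0.026 |

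Fitting three arms with one shared residual variance and averaging the two vadadustat arms changes nothing if those arms share an SD: the contrast multiplier is (¼ + ¼ + 1)/150 = 0.01, as above.

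**Step 3: simulation.** 10,000 ANCOVAs per case, 300 against 150, with baseline Hb and three strata, no missing data, true difference −0.75.

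| SDs (vadadustat/Mircera) | Error, ordinary SE | Error, HC3 | Half-width, ordinary | Half-width, HC3 |
|---|---|---|---|---|
| 1.2/1.2 | 2.4% | 2.3% | 0.236 | 0.238 |
| 0.9/1.2 | 3.8% | 2.5% | 0.199 | 0.220 |
| 0.8/1.2 | 4.3% | 2.5% | 0.188 | 0.214 |
| 1.2/0.9 | 1.5% | 2.2% | 0.219 | 0.200 |

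**Step 4: per-dose comparisons.** As two-group models at 150 against 150, SDs 0.9/1.2 give 2.7% with the ordinary SE and 2.6% with HC3, so there is no real problem. With one residual variance shared over three arms, a pairwise contrast at 0.9/1.2 has an SE ratio of 0.95 and an error of 3.1%.

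**Step 5: power with an unequal-variance SE.** At true difference 0 it is 97.1% or more in every 2:1 case tried, including 210 against 105 with SDs 1.2/1.8.

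**The case against.** **The model is hidden.** A reader might infer that the plan specifies a common-variance ANCOVA. The documents do not show that. The model is defined in Appendix A, whose code is not visible, and the shared SD of 1.2 g/dL is a sample-size assumption. This stands, and it makes the point conditional.

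**The direction is unknown.** A reader might also infer that the false-noninferiority rate is inflated. That requires Mircera to be the more variable arm. The protocol's remark on fewer excursions (3.5.2 and 3.5.3) concerns once-daily vadadustat against darbepoetin, and only values above the range. Other text points the opposite way. The vadadustat group pools two starting doses and changes drug. Protocol 3.4 reports a potential association between higher prior ESA dose and lower Hb response after conversion. In the phase 2 450 mg TIW cohort, 19% withdrew for worsening anemia. If vadadustat is the more variable arm, the interval is conservative for noninferiority. This stands; it is also the reason to choose an estimator that is valid either way.

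**Imputation may soften the error.** The plan analyses all randomized subjects after multiple imputation. If imputation is done by arm, which cannot be confirmed, the between-imputation variance is arm-specific and partly corrects the SE. A check with 30% missing, by-arm imputation, Rubin's rules and no covariates (20,000 runs) gave about 3.1% and 3.4% at ratios 1.2 and 1.4, and 2.6% with equal SDs. So the error may be smaller than in the table, but it does not vanish.

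**A partial check exists.** The per-dose analyses in 6.11.2.1 are robust if fitted as two-group 1:1 models. But they are labelled exploratory and do not correct the interval that carries the decision.

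**The effect is small.** A shift of 0.01-0.04 g/dL against a margin of 0.75 will rarely change the conclusion. This stands.

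**Conclusion.** The point holds conditionally, as a cheap improvement. The SAP made the formal comparison about 2:1, and its readable text does not protect the interval against unequal SDs. If Appendix A uses one common residual variance, the one-sided error is about 3.3% and 3.9% when the Mircera SD is 1.2 and 1.4 times the vadadustat SD (possibly less if imputation is by arm), and about 1.9% and 1.4% with the ratio reversed.

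These figures rest on assumed SD ratios. Different titration rules make unequal SDs plausible but do not establish them or their direction. The shift in half-width is about 0.01-0.04 g/dL, so the noninferiority decision is affected only if the lower limit falls within a few hundredths of -0.75, and superiority only if it falls that close to 0. The protocol's 1:1 per-dose comparisons, fitted as two-group models, do not share the problem, and the power statement is correct.

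**What to change.** Confirm the variance specification in Appendix A. Unless it already allows for unequal variances, state in SAP 6.11.2 and 6.11.3 that the ANCOVA within each imputed dataset uses HC3 standard errors, or a residual variance estimated separately by treatment group, before results are combined by Rubin's rules. Report the residual SD by arm. For the per-dose analyses the change is optional if they are fitted as two-group 1:1 models; if one residual variance is shared over three arms, it should apply there too.

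The cost is one SAP sentence and one option in the code. If the SDs are in fact equal, the efficiency loss is trivial: the simulated half-width goes from 0.236 to 0.238 g/dL. Fixing the choice before arm-level SDs are seen also removes a later analytic decision.
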